1. STATEMENT OF COMPLIANCE

The trial will be carried out in accordance with International Conference on Harmonisation Good Clinical Practice (ICH GCP) and the following:

• United States (US) Code of Federal Regulations (CFR) applicable to clinical studies (45 CFR Part 46, 21 CFR Part 50, 21 CFR Part 56, 21 CFR Part 312, and/or 21 CFR Part 812)

All members of the study team have completed Human Participants Protection and ICH GCP Training.

The protocol, informed consent form(s), recruitment materials, and all participant materials will be submitted to the Institutional Review Board (IRB) for review and approval. Approval of both the protocol and the consent form must be obtained before any participant is enrolled. Any amendment to the protocol will require review and approval by the IRB before the changes are implemented to the study. In addition, all changes to the consent form will be IRB-approved; a determination will be made regarding whether a new consent needs to be obtained from participants who provided consent, using a previously approved consent form.

2. PROTOCOL SUMMARY

2.1	L	SCHEE	DULE O F	Астіліт	TIES (SC	DA)								
Procedures	ElectronicPrescreeningSurvey	RemoteScreening(D0)Remote/in-person	D ay1 ofStimulation(Baseline/D1)In- person	D a y 2 o f S t i m u l a t i o n (D 2) l n - p e r s o n	D a y 3 o f S t i m u l a t i o n (D 3) l n - p e r s o n	D a y 4 o f S t i m u l a t i o n (D 4) l n - p e r s o n	Day5 of Stimulation(D5)In-person	1- we ek foll ow -up FU 1 (D1 2) Re mo te	2- we ek foll ow -up FU 2 (D1 9) in- per son	4- we ek foll ow -up FU 3 (D3 3) Re mo te	6- we ek foll ow -up FU 4 (D4 7) in- per son	8- we ek foll ow -up FU 5 (D6 1) Re mo te	10- we ek foll ow -up FU 6 (D7 5) Re mo te	12- we ek foll ow- up FU 7 (D8 9) Re mo te
Waived/ Verbal Consent	х	х												
Contact information, MDD diagnosis, exclusion/inclu sion criteria	x													
Informed consent			х											
Medication &			х				х		х	х	х	х	х	х
Determine Eligibility		х												
Demographics		X												
Maudsley Staging Method		X												
M.I.N.I.		Х												
C-SSRS Triage HDRS-17		х	X				х		X X		X X			

Procedures	E l e c t r o n i c P r e e n i r g S u u r v e y	RemoteScreening(DO)Remote/in-person	Day1ofStimulation(Baseline/D1)In-person	D a y 2 o f S t i m u l a t i o n (D 2) l n - p e r s o n	Day3 ofStimulation(D3) In-person	Day4ofStimulation(D4)In-person	Day5 of Stimulation (D5) In - person	1- we ek foll ow -up FU 1 (D1 2) Re mo te	2- we ek foll ow -up FU 2 (D1 9) in- per son	4- we ek foll ow -up FU 3 (D3 3) Re mo te	6- we ek foll ow -up FU 4 (D4 7) in- per son	8- we ek foll ow -up FU 5 (D6 1) Re mo te	10- we ek foll ow -up FU 6 (D7 5) Re mo te	12- we ek foll ow- up FU 7 (D8 9) Re mo te
QIDS (S)			Х				Х	Х	Х	Х	Х	Х	Х	Х
ASRM (S)		Х	Х				Х	Х	Х	Х	Х	Х	Х	Х
SHAPS (S)			Х				X	X	X	X	X	X	X	X
DASS-42 (S)			X				X	X	X	X	X	X	X	X
STAL (trait) (S)			X										.,	
STAT (state) (S)			X				X	X	X	X	X	X	X	X
Q-LES-Q-SF (S)	 		X				X	X	X	X	X	X	X	X
			X	V	Y	V	X		X					
			^	^	^	^	^							
Eliaco Side			Y	Y	×	Y	×							
Questionnaire			Â	Â	^	Â	Â							
Likert State														
Scale (Mood)			Х	х	Х	х	х							
(HD)-EEG	1		X1						X ²					
AE Structured	1													
Interview							X							
Treatment														
Experience							х							
Questionnaire														

(S) = RedCap online survey; ASRM: Altman Self-Rating Mania Scale; SHAPS: Snaith-Hamilton Pleasure Scale; DASS-42: Depression Anxiety and Stress Scale; QIDS: Quick Inventory of Depressive Symptomatology; STAI: State-Trait Anxiety Inventory; CGI: Clinical Global Impression Scale; 1. HD-EEG is performed pre-stimulation and post-stimulation; 2. Visit must be done in person for participants undergoing the EEG assessment

	 Change in State-Train Anxiety Inventory (STAI) at D5, FU1, FU2
	 Change in Quality-of-Life Enjoyment and Satisfaction
	Questionnaire, short form (Q-LES-Q-SF) at D5, FU1, FU2
	Change in Clinical Global Impression Scale (CGI) at D5 and FU2
	Exploratory Endpoints:
Endpoints:	 Feasibility - fraction of participants who complete the 5-day
	course of stimulation
	 Change in HD-EEG alpha oscillation power at D1 pre-sumulation, D1 post stimulation, and EU2.
	DI post-stillulation, and FOZ Change in Quick Inventory of Depressive Symptomatology
	(OLIIDS) at EU3_EU4_EU5_EU6_EU7
	 Change in Altman Self-Rating Mania Scale (ASRM) at EU3. EU4
	FU5. FU6. and FU7
	 Change in Depression Anxiety and Stress Scale (DASS-42) at FU3,
	FU4, FU5, FU6, and FU7
	• Change in State-Train Anxiety Inventory (STAI) at FU3, FU4, FU5,
	FU6, and FU7
	• Change in Snaith-Hamilton Pleasure Scale (SHAPS) FU3, FU4, FU5,
	FU6, and FU7
	Change Quality of Life Enjoyment and Satisfaction Questionnaire,
	short form (Q-LES-Q-SF) at FU3, FU4, FU5, FU6, and FU7
	Change in HDRS-17 between FU4 and D1
	We will recruit up to 35 participants (age 18 and older) with a diagnosis of
	unipolar, non-psychotic MDD. Eligible participants will have a HDRS-17 > 8
Study Population:	and low suicide risk (no active intent as determined by the Columbia
	Suicide Severity Rating Scale, C-SSRS, triage form). Participants will be
Dh a st	recruited from the Chapel Hill, Durnam, and Kaleigh areas.
Phase:	N/A
Description of	University of North Constinue of Changel 111
Sites/Facilities Enrolling	University of North Carolina at Chapel Hill
Participants:	

Description of Study Intervention:	We will use the XCSITE100Pro stimulator designed by Pulvinar Neuro for investigational purposes to deliver closed-loop transcranial alternating current stimulation (CLtACS). Stimulation waveforms are sine-waves with a zero-to-peak amplitude of 2mA delivered to F3 and F4 with a return electrode at Cz. Participants will stay in a relaxed yet experimentally controlled state by watching a nature movie such as "Reefscape" during stimulation.
Study Duration:	12 months
Participant Duration:	Participation for each participant will last no longer than 13 weeks total. We estimate total participation time to be approximately 13 hours.

3. INTRODUCTION

3.1 Study Rationale

Major depressive disorder (MDD) is a common, often severe psychiatric illness that affects 6.7% of adults every year in the United States [1]. MDD is characterized by depressed mood, loss of interest or pleasure in activities that used to be enjoyable (anhedonia), sleep disturbances, cognitive impairment, and other symptoms that can severely affect quality of life. Current recommended pharmacological treatments are not effective for all people with MDD and can result in undesirable side effects. Prominently, the STAR*D trial demonstrated that a large percentage of patients are treatment-resistant, and that remission is less likely following multiple drug trials [2]. More effective and safer therapies for the treatment of MDD are desperately needed.

3.2 BACKGROUND

MDD has been associated with hypoactivity in the left dorsolateral prefrontal cortex [3], characterized by elevated alpha oscillations [4]. Therefore, targeting and reducing alpha oscillations in the left dorsolateral prefrontal cortex could prove beneficial to patients with MDD. Targeted stimulation modalities, such as transcranial alternating current stimulation (tACS), can directly engage and modulate oscillatory activity. tACS utilizes sine-wave stimulation waveforms that can enhance specific oscillatory activity [5].

Preclinical and computational studies have contributed to a growing understanding of the mechanism of action of tACS [7]. At the center of successful target engagement is the modulation of neuronal network oscillations by carefully tuned stimulation waveforms that match the endogenous dynamics. Given the low amplitude of the electric field delivered to the brain, modulation of oscillations requires synergistic interaction between the rhythmic stimulation waveform and endogenous brain rhythms [8]. Closed-loop stimulation allows the adjustment of the stimulation to the fluctuations in individual brain network activity patterns and thus is poised to enhance the efficacy in terms of modulating the targeted oscillation. Briefly, closed-loop stimulation combines periodic measurement of brain activity patterns with EEG and stimulation that is tuned based on the dynamic properties of the measured brain activity. Measurement and stimulation are interleaved due to the electric artefacts caused by stimulation. This approach has been pioneered by the [name] Lab and was demonstrated to successfully modulate another, transient thalamo-cortical activity pattern, sleep spindles and associated memory consolidation [9]. Closed-loop stimulation is thus expected to ultimately increase efficacy through improved targeting [10], [11]. Alternative strategies would include increasing the cumulative dose of the stimulation, which would be more burdensome for the participants (longer and or more sessions). Given the promising clinical results of the previous 5-day paradigm, increasing the cumulative dose is not a priority. In

addition, stimulation could be combined with other therapeutic interventions such as therapy. Examining such synergistic effects are outside the scope of this study.

This current study aims to improve efficacy by delivering targeted, individualized stimulation based on closed-loop tACS for which the stimulation waveform is adjusted based on interleaved EEG measurements.

3.3 RISK/BENEFIT ASSESSMENT

3.3.1 KNOWN POTENTIAL RISKS

Risk of Confidentiality Breach: In the unlikely event of a breach of confidentiality, people might discover that an individual was involved in this research study. This is especially sensitive because the clinical population recruited for this study may be subjected to negative consequences caused by the stigma of mental disorders. To avoid breaches in confidentiality, study documents that contain personal information, including the informed consent document, and the document that links study ID numbers to personal identifying information are kept in locked filing cabinets in locked rooms, separate from any source documents containing participant dummy identifiers, or stored in pass-word protected spreadsheets only accessible to study personnel. All data is stored in locked cabinets inside locked offices; electronic data will be stored only on password-protected computers. Interviews will be conducted over the HIPAA approved Zoom account at UNC. Only study personnel will have access to the data. All study staff participate in annual human participant training that includes education about responsibilities to the minimize risk of confidentiality breach.

Risk of Embarrassment: Self-report assessments contain questions regarding sensitive personal information, which may lead to emotions of embarrassment. This risk is necessary in order to assess mood symptoms and associated psychopathology. Participants will be assured upon intake that only study personnel will see any clinical ratings and that self-identifying information will not be collected alongside HIPAA protected information.

Risk of Injury and Discomfort: The side effects of tACS are mild and transient; in fact, low intensity transcranial current stimulation, such as tACS, has been used for several years without any report of serious side effects [12]. Furthermore, this stimulation mode has nothing to do with electroconvulsive therapy that applies many orders of magnitude higher stimulation current. Rather, transcranial current stimulation is so weak that it does not cause super-threshold activation of neurons [13]. However, tACS does have some mild side effects, such as transient mild tingling, burning, or itching under the electrode sites. [6]. To monitor these mild side effects, we will be administering a stimulation questionnaire after each stimulation session to determine whether these effects were experienced and at what intensity. Research personnel are present during the full experiment.

Patients with MDD have an about 20 times higher rate of suicide than average. We have no evidence that our treatment paradigms will in any way increase this likelihood. Rather, active engagement in a clinical trial may offer hope and structure to the participants. Regardless, participants with high suicide risk (intent or plan) will not be included in this study. If an enrolled participant shows signs of suicide risks that were not apparent during enrollment, a referral to UNC Psychiatry will be made. [name], Co-I, will facilitate this process.

We will be using the Columbia Suicide Severity Rating Scale (C-SSRS, triage form) [14] to determine intent for suicide during D1. Inclusion criteria state that the participant must be low suicide risk and that

potential participants with an above "low risk" designation will not be eligible for the study. In the event that suicide risk increases during participation in the study, the participant will be asked to stop the study. The participant will be provided with a referral to UNC Department of Psychiatry, and their mental health care or family medical doctor will be contacted.

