8. STUDY INTERVENTION DISCONTINUATION AND PARTICIPANT DISCONTINUATION/WITHDRAWAL

8.1 DISCONTINUATION OF STUDY INTERVENTION

Discontinuation from the week of stimulation does not mean discontinuation from the study, and remaining study procedures should be completed as indicated by the study protocol. If a clinically

significant finding is identified (including, but not limited to changes from baseline) after enrollment, the investigator or qualified designee will determine if any change in participant management is needed.

The study intervention (i.e., the 5 consecutive days of stimulation) will be discontinued for the following reasons:

- A participant develops significantly increased suicidal risk, as determined by an acute assessment by [name] or [name].
- A participant has an ASRM score greater than or equal to 6.
- The participant misses a single day of stimulation and is unable to make it up at the end of the stimulation week.
- Any clinical adverse event (AE), laboratory abnormality, intercurrent illness or other medical condition, or situation occurs such that continued participation in the study would not be in the best interest of the participant.
- The participant meets any exclusion criteria (either newly developed or not previously recognized).

If the participant withdraws from the intervention, the participant will be contacted and invited for the FU1 survey questionnaires and for the FU2 follow-up assessment including all respective questionnaires. These assessments are not intended as a clinical follow-up with the participants but serve research purposes only.

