9.2 SAFETY AND OTHER ASSESSMENTS

9.2.1 SUICIDAL IDEATIONS AND SUICIDAL BEHAVIOR

Only participants deemed at low suicide risk based on the C-SSRS (ideation allowed, however intent, plan or attempt excluded) are enrolled in this study. The C-SSRS [14] will be administered by trained research personnel at screening and the follow-up session to thoroughly assess suicide risk. In addition, the answers to suicide-related questions on the HRDS-17 and on the QIDS will be monitored. Based on these sources of information, clinical personnel will decide if an acute assessment is required. Acute assessment may include facilitating contact of the participant with their psychiatrist or primary care physician to establish a plan for safety, continued care, and follow-up. If the participant does not have an established provider, [name] or [name] will assist in establishing a care plan. If at any point during the assessment, the participant is deemed an imminent risk of harm to self or others, study personnel will enlist the aid of security at the facility or first responders to ensure that the participant is safely escorted to the Emergency Department for further care. [name] and/or [name] will decide if participation should be stopped after the acute assessment. If the participant is hospitalized, their participation will end.

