9.2.2 DEVELOPMENT OF MANIA

The Altman Self-Rating Mania Scale (ASRM) was designed to assess the severity of manic symptoms at enrolment, with the ability to track changes over the duration of participation. When undergoing treatment for depression, a possible side effect (as inferred from clinical trials with antidepressant medications) is to alter levels of serotonin, potentially associated with mania [18], [19]. Although we do not expect such an event to occur since there are no reports of inducing mania by tACS and we are not using a medication that targets serotonin levels, we will be conducting this assessment as a precautionary measure. If a participant develops any sign of mania (ASRM > 6), [name] or [name] will conduct an acute assessment to determine if the participant is experiencing mania. If this occurs during the week of stimulation, participation in the study will be stopped and their primary mental health care provider or family physician will be contacted. In the case that they do not see anyone for their mental health concerns, [name] or [name] will assist in creating a medical care plan.

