11.1.6 SAFETY OVERSIGHT

Safety oversight will be under the direction of the Principal Investigator [name]. He will review all adverse events timely and serious adverse events and changes in the suicidality and mania ratings as fast as possible. Based on his review, continuation of participant's participation is decided. All SAE or unanticipated AE will be reported to the local IRB and the sponsor.

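### Sections 3.3.1 and 9.2.2 take a participant out of the study where 8.1 stops only stimulation, and the ASRM cut-off differs by one point between sections

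*Combined protocol and SAP*

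**What the plan says.** **Raised suicide risk.** Section 3.3.1 states: "In the event that suicide risk increases during participation in the study, the participant will be asked to stop the study". Section 8.1 lists significantly increased suicidal risk, established by an acute assessment, among the reasons to stop the five days of stimulation. It adds that stopping stimulation is not leaving the study, and that "remaining study procedures should be completed as indicated by the study protocol". Its last paragraph says that after withdrawal from the intervention "the participant will be contacted and invited for the FU1 survey questionnaires and for the FU2 follow-up assessment". In 9.2.1, named persons "will decide if participation should be stopped after the acute assessment", and hospitalization ends participation.

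**Mania.** Section 8.1 gives this reason for stopping stimulation: "A participant has an ASRM score greater than or equal to 6". In 9.2.2 an acute assessment begins at a higher score: "If a participant develops any sign of mania (ASRM > 6". The section continues: "If this occurs during the week of stimulation, participation in the study will be stopped". Section 10.4.4 also uses a score above 6.

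**What depends on these rules.** The primary endpoint is the HDRS-17 change from D1 to FU2 (section 4). The feasibility row of the section 4 table says that this outcome is taken from people who completed stimulation. Section 10.4.4 places the C-SSRS at screening and at the 14-day follow-up, which is FU2. Section 8.2 does not replace people who received stimulation and leave before FU2.

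**The concern.** These are operating instructions for safety events, and staff cannot follow 3.3.1 and 8.1 together. One ends the person's time in the study; the other ends treatment and keeps the person under observation. No text ranks one section above another.

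Two things are at stake. The first is whether someone who triggers a rule before FU2 still has the repeat C-SSRS there. The second is whether some completers lose their FU2 HDRS-17 because their condition changed, in a single-arm before-after comparison with no control group to show the effect of selective loss.

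The two ASRM cut-offs raise a smaller problem of logic. The lower score stops treatment without prompting anyone to look at the participant, while a clinical look is reserved for the higher score.

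**Working it through.** There is no stated figure to reproduce. The check sets the rules side by side and follows them through the visit schedule.

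**1. Do the rules cover the same people?**

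| Trigger | 3.3.1 / 9.2.2 | 8.1 |
|---|---|---|
| Suicide risk | Any increase: asked to leave the study (3.3.1) | Significant increase on acute assessment: stimulation stops, person stays |
| Mania, stimulation week | ASRM > 6 and acute assessment: participation ends (9.2.2) | ASRM >= 6: stimulation stops, person stays |

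During the stimulation week, anyone who meets the suicide trigger in 8.1 also meets the wider one in 3.3.1. Anyone with ASRM > 6 also has ASRM >= 6. So the same person can fall under both rules with opposite dispositions. In 9.2.2 it is unclear whether the stop follows the score or mania confirmed by the assessment. Either reading ends participation where 8.1 does not.

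**2. Where do the cut-offs differ?** For whole-number scores, the set that meets >= 6 but not > 6 is {6}. The Schedule of Activities has the ASRM at D0, D1, D5 and FU1 to FU7, which is 10 ratings. Only D1 and D5 fall in the stimulation week, so the mismatch can act at 2 of 10 ratings, or at most 35 × 2 = 70 ratings in 35 people. At those ratings a score of 6 stops stimulation under 8.1 and triggers nothing under 9.2.2 or 10.4.4.

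**3. Who can be lost from the primary analysis because of the conflict?** Take the section 4 statement that the primary outcome comes from stimulation completers.

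- *Stopped before the last session.* Not a completer under either rule, so outside the primary analysis whichever section is followed. What 3.3.1 or 9.2.2 removes is the FU2 C-SSRS and the other follow-up data.
- *Triggered at D5 after the last session.* A completer. Followed literally, 3.3.1 or 9.2.2 loses the FU2 HDRS-17; continued follow-up keeps it.
- *Raised suicide risk between D5 and FU2.* A completer. No stimulation is left for 8.1 to stop. Section 3.3.1 still asks the person to leave, whereas 9.2.1 makes stopping a decision after the acute assessment.
- *Mania after the stimulation week.* No disposition conflict, because the stop in 9.2.2 is limited to that week.

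**4. What form would the bias take?** Section 10.4.2 specifies a paired t-test. Section 8.3 says the analysis plan allows for missing data, but 10.4.1 to 10.4.3 give no method. A removed completer therefore drops out of the mean. If m of N completers are removed, the observed mean change differs from the full mean by

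(m / N) × (mean change of those kept − mean change of those removed).

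The documents give neither m nor the difference in means, so no size follows. Section 9.2.1 notes that the HDRS-17 contains suicide-related questions. If raised suicide risk goes with less improvement on the HDRS-17, the observed result would look too favourable. For mania the direction is not evident.

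**The case against.** **Most stimulation-week stops cannot affect the primary endpoint.** This stands. A reader might infer that the section followed decides whether everyone who worsens is counted in the primary change score, or might express each removal as lost power. Section 4 does not support that: a person stopped mid-week is not a completer under either rule.

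**Participant safety does not depend on staying in the study.** This also stands. Section 8.1 says its follow-up assessments serve research only. Referral and contact with the treating doctor (3.3.1), acute assessment and emergency escort (9.2.1) and a care plan (9.2.2) do not depend on which stopping rule applies. Section 9.3.4 records adverse events for 7 days, and serious ones for 30 days, after the last day of participation. The loss is of data and consistent handling, not of care.

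**Section 8.1 may not keep people for the whole follow-up.** One sentence refers to all remaining procedures, while the last paragraph names only FU1 and FU2. A reader might infer that nothing is lost under 8.1, but the text assures only FU1 and FU2. Both readings keep FU2, which is what matters here.

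**A reader might also see a conflict over who decides.** Section 9.2.1 gives the decision to named persons; 11.1.6 rests it on the principal investigator: "Based on his review, continuation of participant's participation is decided". Names are removed from the public text, so the investigator may be one of the persons in 9.2.1. The documents do not establish a conflict.

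**The wording in 3.3.1 is a request in a risk narrative, and the ASRM gap is one score.** True, and D1 is the baseline visit, so a 6 there need not show worsening. Even so, 3.3.1 gives an instruction that 8.1 does not share, and 9.2.2 is not phrased as a request.

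**Conclusion.** Two action rules conflict and nothing in the plan reconciles them: leaving the study (3.3.1, 9.2.2) against stopping stimulation and staying for at least FU1 and FU2 (8.1), and ASRM > 6 (9.2.2, 10.4.4) against >= 6 (8.1).

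Possible bias in the primary endpoint is confined to completers removed at D5 after the last session, or for raised suicide risk between D5 and FU2. For earlier stops the cost is the FU2 C-SSRS and follow-up data. The cut-off conflict is confined to a score of exactly 6 at D1 or D5.

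This rests on three assumptions: the primary analysis uses stimulation completers, as section 4 says; 3.3.1 and 9.2.2 are applied as written; and ASRM totals are whole numbers. The documents do not say whether the D5 rating comes before or after that day's session, so the share of D5 triggers that concern completers is unknown. Neither the frequency of triggers nor the size of any bias can be derived. Severity is minor to moderate.

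**What to change.** 1. In 9.2.2 and 10.4.4, use ASRM >= 6 to match 8.1, so that every score that stops stimulation also prompts an acute assessment. Two of the three sections now use > 6; the lower value is proposed because it is the more cautious one already written.

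2. In 3.3.1 and 9.2.2, replace the wording that ends study participation with: *Stimulation stops. Follow-up, including FU2, continues as in 8.1 unless the participant withdraws, is hospitalized, or the persons named in 9.2.1 end participation after the acute assessment.*

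The cost is text edits in three sections, a few extra acute assessments for scores of exactly 6, and some participants being asked to attend follow-up they would otherwise have skipped. They remain free to withdraw. No visit or instrument is added.
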